7. GENERAL CONSIDERATIONS

7.1. REFERENCE START DATE AND STUDY DAY

Study Day will be calculated from the reference start date, and will be used to show start/stop day of assessments and events.

Reference start date is defined as the day of randomization, (Day 1 is the day of randomization).

- If the date of the event is on or after the reference date then:

Study Day = (date of event – reference date) + 1.

- If the date of the event is prior to the reference date then:

Study Day = (date of event – reference date).

In the situation where the event date is partial or missing, Study Day, and any corresponding durations will appear partial or missing in the listings.

7.2. BASELINE

Unless otherwise specified, baseline is defined as the last non-missing measurement taken prior to receiving randomized treatment reference (day of randomization) start date (including unscheduled assessments). In the case where the last non-missing measurement and the randomized treatment start date coincide, that measurement will be considered pre-baseline, but Adverse Events (AEs) and medications commencing on the randomized treatment start date will be considered post-baseline.

For insulin (mealtime, basal and total) levels, baseline is the value collected at Visit 6 (Week 0) which correspond to values collected prior injection of study medication.

7.3. RETESTS, UNSCHEDULED VISITS AND EARLY TERMINATION DATA

In general, for by-visit summaries, data recorded at the nominal visit will be presented. Unscheduled measurements will not be included in by-visit summaries, but will contribute to the scheduled visit if scheduled visit value is missing or the Last Observation Carried Forward (LOCF) value in case primary sensitivity analysis, or best/ worst case value where required (e.g. shift table) in safety analysis.

In the case of a retest (same visit number assigned), the earliest available measurement for that visit will be used for by-visit summaries.

Early termination data will be entered under the Visit 14 (week 18), but for summary tables it will be

Document:	\\sasdata\Mylan\Insulin_glargine\SYA22825\Biostatistics\Documentation\SAP\MYL-1501D-3004_SAP_Final_2_0_clean.doc		
Author:	[name]	Version Number:	2.0
		Version Date:	18OCT2018
Template No:	CS_TP_BS016 Revision 4	Reference:	CS_WI_BS005
Effective Date:	01Apr2016		

Analysis Plan Template

mapped to the next available planned visit number after their last scheduled visit. For example, should a patient discontinue at Visit 9, the Early Termination visit will have their Fasting plasma glucose and their HbA1c assay taken. The fasting plasma glucose would then be summarized under Visit 10 and the HbA1c under Visit 12.

Listings will include scheduled, unscheduled, retest and early discontinuation data.

7.4. WINDOWING CONVENTIONS

Visit windowing will be performed only on HbA1c data. Should a visit have a missing value, the unscheduled visit will be used and mapped by using the following algorithm.

Days to first dose of unscheduled measurement	Mapped Visit
-42 to -28 days	Visit 1 (Week -6 to -4)
-27 to -25 days	Visit 2 (Week -4)
-24 to -18 days	Visit 3 (Week -3)
-17 to -11 days	Visit 4 (Week -2)
-10 to -4 days	Visit 5 (Week -1)
-3 to 3 days	Visit 6 (Week 0)
4 to 10 days	Visit 7 (Week 1)
11 to 17 days	Visit 8 (Week 2)
25 to 31 days	Visit 9 (Week 4)
39 to 45 days	Visit 10 (Week 6)
63 to 75 days	Visit 11 (Week 9)
76 to 91 days	Visit 12 (Week 12)
105 to 119 days	Visit 13 (Week 15)
121 to 133 days	Visit 14 (Week 18)
134 to 147 days	Visit 15 (Week 20)

For subjects who discontinue the study, their early termination HbA1c value will be remapped to their actual visit using the same time window as described above.

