7.4. WINDOWING CONVENTIONS

No visit windowing will be performed for this study.

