16.1.3. PRIMARY ANALYSIS OF PRIMARY EFFICACY VARIABLE

Descriptive statistics will be tabulated by treatment and by time point of the actual HbA1c value and the changes from baseline.

The primary objective of this study is to test the hypothesis that MYL-1501D product from Process VI is non-inferior to MYL-1501D product from Process V based on change in HbA1c from baseline to week 18.

The primary efficacy analysis will be performed for the ITT analysis set.

Mean changes from baseline in HbA1c will be analyzed based on all observed data of schedule visits as well as data imputed using the unscheduled/early termination data (if collected) or MI methodology for schedule visits at which no value is captured (refer to section 16.1.2).

MI will be performed under the assumption of missing-at-random (MAR) and will be implemented in two steps.

First, partial imputation assuming MAR will be carried out to impute intermittent (non-monotone) missing data based on multivariate joint Gaussian imputation model using the Markov chain Monte

Document: \sasdata\Mylan\Insulin_glargine\SYA22825\Biostatistics\Documentation\SAP\MYL-1501D-3004_SAP_Final_2_0_clean.doc

Author: [name]

Version Number:

2.0

Version Date:

18OCT2018

Template No: CS_TP_BS016 Revision 4
Effective Date: 01Apr2016

Reference: CS_WI_BS005

Analysis Plan Template

Carlo (MCMC) method. A separate model will be used for each treatment group. The imputation model will include the pooled investigator sites and basal insulin dose time (morning vs. evening) as fixed covariate and observed HbA1c values at baseline (visit 6), week 12 (visit 12) and week 18 (visit 14). The MCMC method in the MI procedure in SAS will be used with multiple chains, 200 burn-in iterations, and a non-informative prior. In case of non-convergence or non-estimability issues, a ridge prior and single model will be considered with treatment group added as explanatory variable to model.

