16.2.3. ANALYSIS OF SECONDARY EFFICACY VARIABLES

16.2.3.1. Analysis of change from baseline in HbA1c at scheduled visits

Descriptive statistics will be presented for actual and change from baseline to scheduled visits for HbA1c.

Treatment group comparison will be done using the MMRM model as used for the primary endpoint (without imputing the missing values), including treatment, visit, treatment-by-visit interaction, pooled-investigator, basal insulin dosing time, as fixed effects, baseline values as covariate and subjects as random effect.

LSMeans for each treatment group, as well as associated SE and 2-sided 95% CI will be provided by visit. Differences in LSMeans will be calculated and associated 2-sided 95% confidence intervals and p-values will be provided for each visit.

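### SAP 7.3 and 7.4 place the same early-termination HbA1c at different visits, and the 7.4 Week 18 window does not match the protocol's

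*SAP*

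**What the plan says.** **Rule for tables.** SAP V2.0 section 7.3 says that early-termination data are entered under Visit 14 but, in summary tables, are "mapped to the next available planned visit number after their last scheduled visit". Its example is a patient who discontinues at Visit 9: "The fasting plasma glucose would then be summarized under Visit 10 and the HbA1c under Visit 12". The same example stood in SAP V1.0, whose section 7.4 read "No visit windowing will be performed for this study".

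**Rule by day.** V2.0 section 7.4 introduced day windows for HbA1c only, for use when a scheduled value is missing. It adds: "For subjects who discontinue the study, their early termination HbA1c value will be remapped to their actual visit using the same time window". The Visit 13 row is "105 to 119 days" and the Visit 14 (Week 18) row is "121 to 133 days".

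**Where each applies.** Sections 8.3 and 16.1.2 send the primary analysis through the 7.4 windows and then to multiple imputation (MI). The primary model in 16.1.3 contains only Weeks 12 and 18. By-visit HbA1c tables are also required. Section 16.1.3 says "Descriptive statistics will be tabulated by treatment and by time point of the actual HbA1c value and the changes from baseline", and section 16.2.3.1 says "Descriptive statistics will be presented for actual and change from baseline to scheduled visits for HbA1c".

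**Rescue.** Section 16.1.2 treats a Week 18 value as missing after rescue or a switch to the patient's own Lantus. It then says that unscheduled or early-termination data are remapped to Week 18 before MI is applied.

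**Protocol.** Table 1 of protocol V2.0 sets Visit 13 at 112±7 and Visit 14 at 126±7. HbA1c is scheduled at Visits 1, 6, 12 and 14, and not at Visit 13.

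**The concern.** The two rules give different answers for the same blood sample, and neither is stated to take precedence for tables. Section 7.3 is written for summary tables and its example names HbA1c. Section 7.4 is specific to HbA1c and is not limited to the model. Two programmers could each follow the SAP and produce different Week 12 and Week 18 tables. Under 7.3, an HbA1c from about Week 4 would be printed as an observed Week 12 result, while the primary analysis treats that cell as missing and imputes it.

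The Week 18 row is a second, smaller matter. A substitute HbA1c drawn on day 120 is inside the protocol's Week 18 window but cannot fill a missing Week 18 value. One drawn on day 119 is assigned to a visit that has no HbA1c analysis.

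The order of steps in 16.1.2 also leaves open whether a value drawn after rescue or after a switch to own Lantus, just set to missing, could come back into Week 18 through the remapping.

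**Working it through.** **1. Do the 7.4 rows reproduce the protocol windows?** Take centre ± tolerance from protocol Table 1 and compare.

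- Visits 6 to 10 and Visit 13 reproduce exactly (for example 7±3 = 4-10 and 112±7 = 105-119). This shows that 7.4 counts from day 0, as the protocol does.
- Visit 11: 70±7 = 63-77; SAP 63-75.
- Visit 12: 84±7 = 77-91; SAP 76-91.
- Visit 14: 126±7 = 119-133; SAP 121-133, so days 119 and 120 are missing.
- Visit 15: 140±7 = 133-147; SAP 134-147.

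Three protocol days after randomization lie in two windows each. Section 7.4 gives day 77 (Visits 11 and 12) to Visit 12 and day 133 (Visits 14 and 15) to Visit 14, in each case the visit with a scheduled HbA1c. Day 119 (Visits 13 and 14) goes to Visit 13, which has none. Day 120 belongs to Visit 14 alone and has no row.

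If the rows were instead read with randomization as Day 1 (SAP 7.1), 121-133 would be protocol days 120-132, and the days left out would be 119 and 133. Two days are lost on either reading.

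**2. The SAP's own example.** A patient stops around Visit 9 (day 28).

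- Under 7.3 the early-termination HbA1c is tabulated at Week 12 (day 84), which is 84 − 28 = 56 days later.
- Under 7.4 a sample on days 25-31 maps to Visit 9, and one on days 32-38 maps to no row. Week 12 stays empty and is imputed.

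**3. All possible early-termination days, 1 to 126.** Assume that the patient gives an HbA1c on leaving, attends nothing afterwards, and, if leaving later than day 84, attended Visit 12 on day 84.

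| Day of sample | Cell under 7.3 | Cell under 7.4 | Days that differ |
|---|---|---|---|
| 1-75 | Week 12 | neither Week 12 nor Week 18 | 75 |
| 76-84 | Week 12 | Week 12 | 0 |
| 85-91 | Week 18 | Visit 12 row, already filled | 7 |
| 92-120 | Week 18 | Visit 13 (105-119) or no row | 29 |
| 121-126 | Week 18 | Week 18 | 0 |

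The rules differ on 75 + 7 + 29 = 111 of 126 days and agree on 9 + 6 = 15. With Visit 12 on day 77 the count is 75 + 43 = 118; on day 91 it is 75 + 29 = 104. These are calendar days, not patients.

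**4. What one lost Week 18 value could do.** Inputs: SD 0.74 and 202 planned subjects (protocol 7.1), margin 0.4. The approximate 95% half-width is 1.96 × SD × √(4/N).

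- N = 202: 1.96 × 0.74 × √(4/202) = 0.2041
- N = 201: 1.96 × 0.74 × √(4/201) = 0.2046
- Difference: about 0.0005

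This treats the subject as wholly lost, although MI would still use the baseline and any Week 12 value. If the imputed value lay a full SD from the discarded one, the arm mean would move by 0.74/101 = 0.007.

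**The case against.** The best reply is that nothing is ambiguous where it counts. Sections 8.3 and 16.1.2 both route the primary analysis through 7.4. Section 7.4 is the later rule and is specific to HbA1c, while 7.3 opens as a general rule, so the example is an uncorrected leftover from V1.0. This stands for the primary analysis. It does not settle the tables, because 7.3 is itself specific to tables and its retained example names HbA1c.

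A second reply is that table and model could never match in full: the model runs on 100 completed datasets, and 16.1.2 sets some observed Week 18 values to missing. That is true, but those differences are declared. Showing an early HbA1c as an observed Week 12 or Week 18 result is not.

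Third, day 119 is a tie-break and not an omission, since it lies in both protocol windows. That is correct. The overlap arises in Table 1 itself, where Visit 13 is labelled Week 15 but carries day 112 (15 × 7 = 105). Only day 120 is a plain gap. The tie-break is still the less useful choice, and it runs against the way 7.4 settles days 77 and 133.

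**Conclusion.** The point holds as a correction to the SAP text. The two rules conflict for the by-visit HbA1c tables, and the Week 18 row does not match the protocol. It concerns only patients without a scheduled Week 12 or Week 18 value who have an unscheduled or early-termination HbA1c. The effect on the treatment difference is negligible on the figures above, and no change in the non-inferiority conclusion is claimed.

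Three stronger readings are tempting and are not supported:

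- **That the non-inferiority result depends on which rule is chosen.** The primary analysis has one rule, 7.4.
- **That Week 18 samples taken on days 119 or 120 are discarded.** A nominal Visit 14 sample on those days is still Week 18; the windows apply only to substitute values.
- **That a patient count can be obtained by applying the 15% in protocol 7.1 to 202 subjects.** That figure is an allowance for ineligibility for the per-protocol analysis, not a dropout rate. Protocol 6.3.7 also means that not every early leaver gives a sample, and that those who only stop study drug are asked to attend the remaining visits. The documents give neither the number nor the timing of early-termination HbA1c values.

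Leaving values from days 92-118 to MI follows from the window rule and is not disputed.

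**What to change.** Before unblinding:

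- Make 7.4 the single HbA1c mapping rule for tables and models, and take HbA1c out of the next-visit example in 7.3.
- Set the Week 18 window to 119-133, with day 119 going to Visit 14 because HbA1c is scheduled there.
- Either align the Week 12 window with the protocol (77-91) or state that day 76, which the protocol gives to Visit 11 alone, is included on purpose.
- State whether the window days count from day 0 or from Day 1.
- Reword 16.1.2 so that it is clear whether a value drawn after rescue or a switch to own Lantus, treated there as missing, can be remapped into Week 18.

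The cost is SAP wording and one derivation change, with no change to data collection. The main gain is that tables and model follow one rule; the wider Week 18 window will recover few values, if any.

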7.5. STATISTICAL TESTS

The default significant level will be (5%); confidence intervals will be 95% and all tests will be two-sided, unless otherwise specified in the description of the analyses.

Non-inferiority will be tested at 2.5% (one-sided) level of significance.

Document: \sasdata\Mylan\Insulin_glargine\SYA22825\Biostatistics\Documentation\SAP\MYL-1501D-3004_SAP_Final_2_0_clean.doc

Author: [name]

Version Number:

2.0

Version Date:

18OCT2018

Template No: CS_TP_BS016 Revision 4
Effective Date: 01Apr2016

Reference: CS_WI_BS005

7.6. COMMON CALCULATIONS

For quantitative measurements, change from baseline will be calculated as:

- Test Value at Visit X – Baseline Value

7.7. SOFTWARE VERSION

All analyses will be conducted using SAS version 9.4 or higher.

8. STATISTICAL CONSIDERATIONS

8.1. ADJUSTMENTS FOR COVARIATES AND FACTORS TO BE INCLUDED IN ANALYSES

The following covariates and factors are used in the analyses. For details of their inclusion in the models, see the specific analysis section.

- Pooled sites
- Time of Glargine administration (morning, evening), stratification factor.
- Baseline HbA1c (continuous variable)

8.2. MULTICENTER STUDIES

This study will be conducted by multiple investigators at multiple centers in the USA.

When specified, statistical analysis will be adjusted for pooled sites based on US census regions.

All sites are grouped by state.

All states within a US census region (Northeast, Midwest, South, West, Pacific) with fewer than 8 randomized patients will be combined into a single pooled site for analysis purposes. The maximum number of subjects can not exceed 40 per site.

The pooled method will be as follow (performed manually):

Sites within a census region (New England, Midwest, South, West) with less than 8 randomized patients will be pooled with the closest sites within the same census region until they reach at least 8 subjects.

Document: \sasdata\Mylan\Insulin_glargine\SYA22825\Biostatistics\Documentation\SAP\MYL-1501D-3004_SAP_Final_2_0_clean.doc

Author: [name]

Version Number:

2.0

Version Date:

18OCT2018

Template No: CS_TP_BS016 Revision 4
Effective Date: 01Apr2016

Reference: CS_WI_BS005

Analysis Plan Template

Pooled Site Group	Site ID (number of subjects per site)	Total Number of Subjects
Pool_1 (Midwest_1)	40016 (2), 40029 (2), 40038 (1), 40059 (2), 40074 (1), 40097 (2), 40098 (2), 40100 (1)	13
Pool_2 (Midwest_2)	40083 (3), 40086 (1), 40095 (5)	9
Pool_3 (North_1)	40040 (3), 40051 (2), 40062 (2), 40087 (3), 40096 (2), 40103 (1)	13
Pool_4 (South_1)	40009 (2), 40019 (1), 40026 (1), 40027 (1), 40035 (3), 40048 (4), 40057 (3), 40077 (4)	19
Pool_5 (South_2)	40012 (5), 40024(1), 40050 (4), 40078 (6)	16
Pool_6 (South_3)	40047 (4), 40075 (2), 40084 (1), 40106 (2)	9
Pool_7 (South_4)	40018 (2), 40030 (3), 40042 (1), 40054 (3), 40107 (1)	10
Pool_8 (South_5)	40025 (2), 40036 (3), 40037 (4), 40056 (2), 40108 (1)	12
Pool_9 (South_6)	40001 (4), 40004 (8), 40017 (3), 40033 (2), 40045 (3), 40046 (4), 40070 (3), 40088 (1), 40111(1)	29
Pool_10 (West_1)	40003 (3), 40005 (2), 40008 (6), 40014 (2), 40022 (1), 40049 (2), 40060 (3), 40061 (2), 40064 (2), 40071 (6), 40081 (3), 40082 (2), 40090 (3)	37
Pool_11 (West_2)	40021 (3), 40043 (2), 40079 (2), 40091 (6)	13
Pool_12 (West_3)	40020 (5), 40053 (3)	8
Pool_13 (West_4)	40011 (13), 40015 (6), 40092 (4)	23
Pool_14 (West_5)	40089 (4), 40093 (4)	8

8.3. MISSING DATA

After having mapped data captured at unscheduled and/or early termination visits (if any) to schedule missing visits using visit windows technique (refer to [section 7.4](#)), missing primary data will be imputed by using the multiple imputation (MI) technique (see [section 16.1.3](#)).

As another sensitivity analysis, the imputed values by MI will be corrected such that the full non-inferiority margin will be added for imputed values in Process VI group.

A sensitivity analysis using Last Observation Carried Forward (LOCF) will also be performed on the primary efficacy parameter.

In the secondary efficacy data, the weight used in the daily total insulin will be imputed by the weight of the previous visit value if current weight value is missing.

Document: \sasdata\Mylan\Insulin_glargine\SYA22825\Biostatistics\Documentation\SAP\MYL-1501D-3004_SAP_Final_2_0_clean.doc

Author: [name]

Version Number:

2.0

Version Date:

18OCT2018

Template No: CS_TP_BS016 Revision 4
Effective Date: 01Apr2016

Reference: CS_WI_BS005

8.4. MULTIPLE COMPARISONS/ MULTIPLICITY

No adjustment for multiplicity will be performed.

8.5. ACTIVE-CONTROL STUDIES INTENDED TO SHOW NON-INFERIORITY OR EQUIVALENCE

Non-inferiority will be established if the upper bound of a two-sided 95% confidence interval (CI) for the absolute difference (MYL-1501D Process VI minus Process V) of mean change from baseline to week 18 for HbA1c is less than or equal 0.4%.

8.6. EXAMINATION OF SUBGROUPS

Subgroup analyses will be conducted as stated in the exploratory analysis sections. It should be noted that the study was not designed to detect treatment differences with high statistical power within subgroups.

The following subgroups will be assessed and described within the subgroup analysis sections (16.2.4). A minimum of 8 subjects/arm in each subgroup is needed. For subgroup with less than 8 subjects/arm, this subgroup will be pooled with the other ones having less than 8 subjects/arm together and the subgroup will be named "other" if there are other subgroups with less than 8 subjects/arm exist.

- Gender:
 - o Female
 - o Male
- Age (years):
 - o ≤ 21
 - o > 21 to <65
 - o ≥65
- Race in 5 categories:
 - o American Indian or Alaska Native
 - o Asian
 - o Black or African American
 - o Native Hawaiian or Other Pacific Islander
 - o White
- Ethnicity in 2 categories:

Document: \sasdata\Mylan\Insulin_glargine\SYA22825\Biostatistics\Documentation\SAP\MYL-1501D-3004_SAP_Final_2_0_clean.doc

Author: [name]

Version Number:

2.0

Version Date:

18OCT2018

Template No: CS_TP_BS016 Revision 4
Effective Date: 01Apr2016

Reference: CS_WI_BS005

Analysis Plan Template

- o Hispanic or Latino
- o Not Hispanic or Latino
- o Not reported or Unknown

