4.2 Inclusion and Exclusion Criteria

4.2.1 Inclusion Criteria

Subject eligibility should be reviewed and documented by an appropriately qualified member of the investigator's study team before subjects are included in the study.

Subjects must meet all of the following inclusion criteria to be eligible for enrolment into the study:

1. Written and signed informed consent needs to be provided by subjects or their legal representatives before starting any protocol-specific procedures.
2. Male and female subjects between the ages of 18 to 65 years, both ages inclusive.
3. Subjects with an established diagnosis of T1DM per American Diabetes Association (ADA) 2017 criteria who also fulfil the following criteria:
 - a. Initiation of insulin treatment within 6 months of T1DM diagnosis
 - b. Treatment with basal-bolus insulin therapy for at least 1 year before screening
 - c. Fasting plasma C-peptide <0.3 nmol/L (0.9 ng/mL) at screening
 - d. Subject has been on once daily Lantus® or once daily Levemir® or once daily Toujeo® at stable dose ($\pm 15\%$ variation in dose) for at least 3 months at screening
4. Body mass index (BMI) of 18.5 to 35 kg/m² at screening (both values inclusive).
5. Stable weight, with no more than 5 kg gain or loss in the 3 months prior to screening, this information will be collected by subject interview during medical history.
6. HbA1c $\leq 9.5\%$ at screening.
7. Hemoglobin ≥ 9.0 g/dL at screening.
8. Subject has the capability of communicating appropriately with the investigator.
9. Subject is able and willing to comply with the requirements of the study protocol including the 8-point SMBG, completion of subject diary records and following a recommended diet and exercise plan for the entire duration of the study.
10. Female subjects of childbearing potential who are willing to use oral contraception or acceptable methods of contraception, (e.g., intra-uterine device, spermicidal gel plus

condom, diaphragm plus condom, etc.), from the time of screening and for the duration of the study, through study completion.

- a. Periodic abstinence (e.g., calendar, ovulation, symptothermal, post-ovulation methods) and withdrawal are not acceptable methods of contraception.
- b. Postmenopausal females must have had no regular menstrual bleeding for at least 1 year prior to screening.
- c. Female subjects who report surgical sterilization must have had the procedure at least 6 months prior to screening.

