7.2.6 Sub-Group Analyses

Subgroup analyses of important factors, including but not limited to factors such as age group, gender and race are planned for the key outcomes of HbA1c and immunogenicity variables. These will be conducted by adding factor and treatment-by-factor interactions to the MMRM model models of the main analyses. Other exploratory subgroup analyses may be performed, as deemed appropriate.

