11. DEMOGRAPHIC AND OTHER BASELINE CHARACTERISTICS

Demographic data and other baseline characteristics will be presented for the RND and SAF populations.

The continuous demographic/baseline variables will be summarized using the mean, median, standard deviation, minimum, and maximum values. For categorical (nominal) variables, the number and percentage of patients will be used. No statistical testing will be carried out for demographic or other baseline characteristics. All demographic and baseline characteristics will be presented in a listing.

The following demographic and other baseline characteristics will be reported for this study:

- Age (years) - calculated relative to date of informed consent
- Gender
- Race

Document: \sasdata\Mylan\Insulin_glargine\SYA22825\Biostatistics\Documentation\SAP\MYL-1501D-3004_SAP_Final_2_0_clean.doc

Author: [name]

Version Number:

2.0

Version Date:

18OCT2018

Template No: CS_TP_BS016 Revision 4

Reference: CS_WI_BS005

Effective Date: 01Apr2016

Copyright © 2009, 2010, 2012, 2016 Quintiles Transnational Corp. All rights reserved.

The contents of this document are confidential and proprietary to Quintiles Transnational Corp. Unauthorized use, disclosure or reproduction is strictly prohibited.

Analysis Plan Template

- Ethnicity
- Weight (kg)
- Height (cm)
- BMI (kg/m²)
- Duration of diabetes (years)
- Time of glargine administration (morning, evening)
- Baseline fasting plasma glucose (mmol/L)
- Baseline HbA1c (%)
- Insulin use prior to screening (yes, no)
- Fasting C-Peptide, HIV, HBsAg and HCVAb (positive, negative)

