16.2.4. SUBGROUP ANALYSIS

The effect of subgroups mentioned in [section 8.6](#) on the change from baseline HbA1c at week 18 will be examined by employing a MMRM model. The subgroups will be included in the model along with the treatment group. Additionally separate subgroup analysis within each subgroup mentioned in [section 8.6](#) will be performed same MMRM model for treatment comparison within each subgroups.

The similar subgroups will also be examined for the immunogenicity parameters for the percent binding and the incidence analysis of cross reactive antibody. Besides examine subgroup by treatment interaction for percent binding. Separate analysis for both percent binding and incidence will be performed for treatment comparison within each subgroup.

Document:	\sasdata\Mylan\Insulin_glargine\SYA22825\Biostatistics\Documentation\SAP\MYL-1501D-3004_SAP_Final_2_0_clean.doc		
Author:	[name]	Version Number:	2.0
		Version Date:	18OCT2018
Template No:	CS_TP_BS016 Revision 4	Reference:	CS_WI_BS005
Effective Date:	01Apr2016		

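### The SAP's age bands do not fit an 18–65 trial: the ≥65 band holds only 65-year-olds, and the small-group rule either pools them with the ≤21s or leaves them with no stated handling

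*SAP*

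**What the plan says.** SAP V2.0 section 8.6 defines three age bands: ≤21, >21 to <65, and ≥65 years. It sets a size condition, "A minimum of 8 subjects/arm in each subgroup is needed", and for a group that falls short, "this subgroup will be pooled with the other ones having less than 8 subjects/arm together". The combined group is labelled as other. Pooling is conditional on a second small group existing. The rule does not mention adjacency, a single small group, or a pooled group that is still below 8 per arm.

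Protocol V2.0 section 4.2.1 admits "Male and female subjects between the ages of 18 to 65 years, both ages inclusive". SAP section 11 fixes the reference date: "Age (years) - calculated relative to date of informed consent".

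Protocol section 7.2.6 says that subgroup analyses, "including but not limited to factors such as age group, gender and race are planned for the key outcomes of HbA1c and immunogenicity variables", and gives no age cut-points. Under SAP section 16.2.4, "The subgroups will be included in the model along with the treatment group", and the same MMRM is also fitted separately within each subgroup. Section 8.6 carries a caveat: "It should be noted that the study was not designed to detect treatment differences with high statistical power within subgroups".

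**The concern.** The upper cut-point sits at the very top of the eligible range, so the top band is one year of age wide. The middle band takes nearly all of the range. The two bands most likely to be sparse are the opposite ends, and the pooling rule would join exactly those two. A treatment difference in a group made of 18–21-year-olds and 65-year-olds cannot be read as an age effect in either direction.

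At stake is the one age analysis the protocol names, for HbA1c and for immunogenicity. If the bands are applied as written, the report may show a middle group that is close to the whole trial beside a group with no age meaning, or a band whose treatment the analyst has to decide case by case.

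**Working it through.** **The plan's own figures.** Section 8.6 states no numerical result, so the sample size is the figure to reproduce. The inputs are margin 0.4, true difference 0.03, SD 0.74, one-sided 2.5% and 90% power (Protocol 7.1, SAP 7.5). The normal formula gives n per arm = 2 × (1.960 + 1.282)² × 0.74² / (0.4 − 0.03)² ≈ 84.1, so 85. With the t distribution, 85 per arm gives power 0.8999 and 86 gives 0.903, which matches 86 per arm (172). Then 172 / 0.85 = 202.4, against 202 planned. The inputs are sound to use below.

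**Width of the bands, no assumption needed.** Ages 18 to 65 inclusive are 48 whole years. The ≤21 band covers 4 of them (18–21), the middle band 43 (22–64) and the ≥65 band 1.

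**Expected sizes, assuming uniform ages.** With 202 subjects:
- age 65: 202 × 1/48 = 4.2 (2.1 per arm)
- ≤21: 202 × 4/48 = 16.8 (8.4 per arm)
- middle: 202 × 43/48 = 181 (90%)

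**Chance that the age-65 band meets the minimum.** I read the rule as requiring 8 in each arm, so the probability is P[Bin(101, p) ≥ 8]². For p = 1/48 this is 1.7 × 10⁻⁶; for p = 4% it is 0.0025.

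**Chance that the ends merge.** The age-65 band is almost always small, so merging happens when the ≤21 band is also small. The merge probability is then close to 1 − P[Bin(101, p) ≥ 8]², with p the share aged ≤21. Simulation of both bands together (200,000 draws, about 2% aged 65) agrees for the first four rows. The last row is the complement only.

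| Share ≤21 | ≤21 reaches 8 in both arms (age-65 band alone) | Ends merged | Merged group still below 8 in an arm, given merged |
|---|---|---|---|
| 4% | 0.002 | >0.99 | 0.93 |
| 6% | 0.07 | 0.93 | 0.73 |
| 8.3% (uniform) | 0.37 | 0.63 | 0.48 |
| 10% | 0.64 | 0.36 | 0.39 |
| 12% | 0.86 | 0.14 | not computed |

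**Sensitivity to the sample size.** The pooled-site table in SAP section 8.2 sums to 13 + 9 + 13 + 19 + 16 + 9 + 10 + 12 + 29 + 37 + 13 + 8 + 23 + 8 = 219. With 109 per arm the merge probability is 0.52 under uniform ages and 0.89 with 6% aged ≤21 and 2% aged 65.

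**Precision.** The 95% half-width within a group of n per arm is 1.96 × 0.74 × √(2/n):
- n = 8: 0.73 (0.79 with the t quantile), against a margin of 0.4
- n = 90 (middle band): 0.22
- n = 101 (whole trial): 0.20
- n = 50 (half the trial): 0.29

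For the difference in effect between two groups, 1.96 × 0.74 × √(2/a + 2/b) gives 0.76 for 8 versus 93 per arm and 0.41 for two equal halves. These figures ignore covariate adjustment. The within-subgroup MMRM also fits 14 site pools. Sixteen subjects drawn at random from the 219 fall in about 9 pools on average, leaving roughly 16 − 9 − 3 = 4 between-subject degrees of freedom after baseline, dose time and treatment. The 0.73 is therefore optimistic.

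**The case against.** The strongest reply is that these are exploratory analyses whose limits are already disclosed in section 8.6, and that protocol section 7.2.6 allows further subgroup analyses as needed, so a better age split could be added at any time. That stands as a limit on the harm. It does not answer the point: low power is admitted, but cut-points that miss the eligible range and a pooling rule that joins opposite ends are separate faults, and a split added later is not pre-specified.

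Three stronger readings are tempting, and the documents do not support them.
- A reader might infer that the age analysis is bound to be uninformative. If the ≤21 band reaches 8 per arm it is not pooled and is a coherent young-adult group, though imprecise. That chance runs from 0.002 to 0.86 as the share aged ≤21 goes from 4% to 12%, so no single figure should be carried forward.
- A reader might infer that a lone age-65 band breaches the SAP's own minimum. The text is silent; leaving that band unanalysed is equally consistent with it. This is an ambiguity.
- A reader might infer a conflict between protocol and SAP. The protocol gives no age cut-points, so there is none.

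It is also fair to say that the statement about age 65 holds for eligible subjects only. The ITT set keeps randomized subjects who do not comply with the protocol, so an over-age enrolment would fall in that band.

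**Conclusion.** The point holds as a minor flaw in a supportive analysis. From the text alone, the ≥65 band means age 65 for eligible subjects, the middle band spans 43 of 48 eligible ages, and the pooling rule can merge the two ends or leave one without a partner. Given that the age-65 band is sparse, which is close to certain unless 65-year-olds are unusually common, one of those two outcomes must follow.

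Which one depends on an age distribution the documents do not give. Merging is the likelier outcome when fewer than about 8% are ≤21, and the lone age-65 band becomes likelier near 10% or above. Under uniform ages the middle band nearly repeats the overall result. The primary non-inferiority test, its sensitivity analyses and its type I error are untouched.

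**What to change.** Amend SAP section 8.6 before unblinding, in three respects:
1. Replace the age bands with cut-points inside 18–65 that give usable group sizes. A split at the blinded median age is one example; the documents do not favour any particular cut.
2. For an ordered factor such as age, pool a sparse level only with the adjacent level.
3. State what happens when a single level is sparse, and when a pooled level is still below 8 per arm.

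The cost is SAP wording. No protocol amendment is needed, because the protocol names age group without cut-points. The price is that the extremes of age are no longer shown separately, and a younger-versus-older split answers a different question from one that isolates the ends.
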